4.2 Targeting effect

H2: We hypothesize that the overall effect of the JIC is strongest under edge-central targeting, intermediate under indegree targeting, and weakest under random targeting.

We estimate the contribution of targeting to the overall effect with the following equation:

$$Y_{ij} = \beta_0 + \beta_1' S_j + \beta_2 X_{ij} + \epsilon_{ij}$$

where S_j is a vector of indicator variables for random, indegree, and edge central targeted schools, and differences between the elements of β_1 evaluate the differences between targeting strategies.

4.3 Network estimands

Guided by the same hypotheses as above, we also estimate total, spillover, and direct effects of the JIC on the same outcomes, and compare them across targeting strategies. We estimate the total effect of the JIC on targeted students separately for the three targeting strategies analogous to equation (1), except that we now restrict the samples to treated students in treated schools and comparable untreated students in control schools.⁴ We estimate the spillover effect of the JIC on non-targeted students separately for the three targeting strategies analogously to equation (1), except that we now restrict the samples

⁴Specifically, under random targeting, we compare randomly targeted students in treated schools to all students in untreated schools; under indegree targeting, we compare treated students in indegree-treated schools to the corresponding share of highest-indegree students in untreated schools; under edge-centrality targeting, we compare treated students in edge-centrality schools to the corresponding share of highest edge-centrality pairs in untreated schools.

to untreated students in treated schools and comparable untreated students in control schools. We estimate the direct effect of the JIC on targeted students under random targeting, except that we now restrict the sample to students in random-targeted schools, and estimate

$$Y_{ij} = \beta_0 + \beta_1 T_{ij} + \beta_2' X_{ij} + \epsilon_{ij},$$

where T_{ij} is an indicator equal to 1 if student i in random-targeted school j is treated and 0 otherwise.

The direct effect compares treated students in treatment schools to comparable un-treated students in treated schools. By comparing treated to untreated students in the same school, this effect removes the indirect effect via peers. Note: in our study, however, the direct effect can only be estimated with random targeting, because only with random targeting are treated and untreated students in a given school comparable to each other.

We compare the effectiveness of targeting strategies on the total, spillover, and direct effect at the school level by estimating models analogous to equation (2) without covariate controls on the appropriately restricted samples. We note that since the subsamples of treated (or untreated) individuals in the three targeting arms are not comparable, un-adjusted comparisons warrant a causal interpretation only at the group level, and require covariate control (analogous to equation 2) to be interpreted as averages of individual effects.

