Pre-Analysis Plan:

Assessing the impact of the HIV prevention tool “Join-In-Circuit on AIDS, Love & Sexuality” in Zambia

[name] and [name]*

*Corresponding author: I received valuable feedback from [name], [name] and [name]. Please send correspondences to [name] at [contact].

Contents

1	Background	3
2	Design	4
2.1	Population	4
2.2	Randomization	6
3	Surveying	8
3.1	Baseline	8
3.2	Network mapping	9
3.3	Outcome measurement	10
3.4	Endline	10
4	Empirical Analysis	10
4.1	Overall effect	11
4.2	Targeting effect	12
4.3	Network estimands	12
4.4	Robustness	13
5	Final remarks	14
6	Supplementary Information	14
6.1	Blocking code	14
6.2	Survey instrument	15

11 Background

In Zambia, 13% of the 15 to 49 year old population lives with HIV. The highest number of new HIV infections is among young people (Central [Statistical Office \(CSO\) \[Zambia\]](#), [2015](#)). To counter the spread of the disease, developmental and governmental actors are increasingly relying on educational behavior change tools. A particularly widely used tool, implemented by the German Development Corporation (henceforth, GIZ), is the so-called “Join-In-Circuit on AIDS, Love Sexuality” (JIC). The JIC uses exercises, pictorial aids and edutainment strategies in an interactive circuit with six stations to teach kids about HIV. The tool aims to improve a) HIV and sexual reproductive health knowledge, b) HIV testing uptake, and c) demand for health services. Previous research ([name] [and Wong-Grunwald, 2017](#)) has investigated the direct effect of the JIC on knowledge about STIs as well as self-reported sexual behavior in Zimbabwe, and has found positive effects in both domains.

The present research project evaluates the JIC in Zambia. We randomly assign 170 participating schools to five different JIC treatment arms. The first two arms represent control schools. Here, no JIC will be implemented. The third arm implements the JIC among a random subset of students. The fourth arm implements the JIC among indegree central students. The fifth arm implements the JIC among edge betweenness central students. In each school, the JIC will be implemented in one pre-determined grade. Within each school at least 30 students will be selected. For larger schools, 20 per cent of students in the selected grade are selected.

The design allows us to tackle four distinct questions:

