2.1 Population

The study's population is the full universe of schools in the Choma and Livingstone provinces of Zambia (a total of 218 schools). The schools were provided to the authors by the Zambian Ministry of Education. 28 schools were randomly selected for a pre-test RCT (randomly assigning 14 schools to treatment, and 14 schools to control). For this reason, the final number of schools analyzed in this study is 204 (excluding already treated schools from the pilot RCT). The schools are split between primary (grade 1 to 7) and secondary schools (grade 8 to 12). In order to not interfere with exam periods, the Ministry of General Education and GIZ decided to implement the JIC among children in grade 6 in primary schools, and grade 11 in secondary schools. Before the intervention, we contacted all 204 eligible schools. During this process, several schools were found to not exist, to be double-counted or to be a different institution altogether (e.g., kindergartens mislabeled as primary schools). The final set of schools was then 170.

The descriptive statistics of the school sample is given in Table 1. On average, the schools have 80 students¹ and 74 percent of the sample are in Choma. 88 percent of schools are considered rural, i.e., they do not lie in a major town. 4 percent of the sample have received a JIC before. The school's funding is as follows. The vast majority (80 percent) are funded by the Government of the Republic of Zambia (GRZ).

¹We caution that the data behind this variable is highly noisy and based on estimates. For this reason, the data was not used when implementing our block-randomization scheme.

3 percent are funded by the community, 12 percent are privately funded and 5 percent are funded through non-standard grants. Schools' access to governmental and health facilities is captured by three variables. First is the distance to the nearest District Board of Education (DEBS, average of 36 kilometers). Second is the distance to the nearest so-called youth-friendly corner (YFC, average of 20km). Third is the distance to the nearest health facility (HF, average of 4km).

Table 1: Descriptive Statistics of Schools

		N	Mean	SD
School characteristics				
	Students	169	79.0	58.4
	Choma	170	73.5	44.2
	Primary	170	88.2	32.3
	Rural	170	60.0	49.1
	JIC before	170	3.5	18.5
Funding				
	GRZ	157	80.3	39.9
	Community	157	3.2	17.6
	Private	157	12.1	32.7
	Grant	157	4.5	20.7
Location				
	Lat	160	-16.8	2.8
	Lon	160	26.6	0.6
Facilities				

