3.1 Baseline

The baseline data collection, conducted by a team of 10 trained enumerators divided into 3 groups, lasted about two months from March 16, 2017 to April 11, 2017 and from May 24, 2017 to July 11, 2017 for a total of 52 days. Data collection had to be interrupted during the month of April due to a month-long school break. The survey instrument is attached to this document. The prime reason for the baseline survey—in addition to collecting outcomes before the intervention takes place—was to map the entire friendship network in a given grade (more below).

Once data collection started, the survey team found additional ineligible schools that were either unreachable by car, did not have the targeted grades or were closed. Overall, the survey team managed to conduct a baseline in 98 out of the 102 schools in the treatment group (96% of the target), 28 out of 34 schools in the control 1 category, and 7 out of 34 in control 2. The final sample, thus, consists of 133 schools for the baseline survey. 37 of the schools are in Livingstone and 96 schools in Choma. 19 schools are secondary schools and 114 are primary schools. All students in either grade 6 (if primary school) or grade 11 (if lower secondary school) present on the day of baseline were interviewed for a total of 8,276 students.

Since some instruments are sensitive in nature (more below), we opted to administer self-administered surveys on tablet computers supported by ACASI (audio-assisted computerized assisted self-interview software) technology. Specifically, the survey was loaded unto the tablets and each question was accompanied by an audio file that read out loud the question in the desired language (options were Tonga and English). Students were given headphones for increased privacy. After hearing the question, students were to tap on the relevant answer. Finding the correct answer was facilitated by a) maximizing the number of questions with a vignette or picture or color coded, and by

b) positioning the answers on the left, middle, or right panel of the tablet and have the audio file explain where to find the answer. Two enumerators were present to help and assist in case of confusion or any other problem.

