4.4 Robustness

To ensure that our estimates are robust, we commit to the following additional checks. Specifically, we will re-run the above analyses

1. Excluding all covariates

2. Using randomization inference

15 Final remarks

We commit to:

- 1• Make all data and code available after the initial publication of any academic paper or 2 years after the experiment is finished, whichever comes first.
- 2• Answer any questions pertaining to our analysis or to this document.
- 3• Make any deviations from this PAP explicit in the paper.

16 Supplementary Information

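### Under random targeting, the total effect compares about 30 students per treated school with the whole grade in control schools, unweighted, so the two sides weight schools by size differently

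*SAP*

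**What the plan says.** The SAP Background section sets the selection rule: "Within each school at least 30 students will be selected. For larger schools, 20 per cent of students in the selected grade are selected".

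Section 4.3 estimates the total effect with equation (1) of section 4.1, on samples restricted to treated students and comparable control students. Equation (1) is student-level ordinary least squares with standard errors clustered by school, and no weights are mentioned. Footnote 4 defines the comparable controls. For random targeting, "under random targeting, we compare randomly targeted students in treated schools to all students in untreated schools". For the two centrality arms, the same footnote takes only the matching share of the most central students in control schools.

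For spillover, section 4.3 restricts the sample "to untreated students in treated schools and comparable untreated students in control schools". It does not say who counts as comparable under random targeting.

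The school covariates in footnote 3 include Students, Primary, Rural and three distances. Footnote 1 warns that the student counts are noisy estimates. The first robustness check in section 4.4 is "Excluding all covariates".

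**The concern.** Random selection within a school makes the selected students exchangeable with the other students of that school. It does not make the pooled selected students exchangeable with the pooled control students, because the selected fraction falls as the grade grows. A treated grade of 150 contributes 30 students to the total-effect sample. A control grade of 150 contributes 150.

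If outcomes differ between small and large grades, part of that difference enters the random-arm total effect. The plan mirrors the selection share on the control side for the centrality arms but not for this arm. What is at stake is the random-arm answer to research question 2 and, depending on how the spillover comparator is read, to question 3.

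**Working it through.** **Inputs from the SAP**
- Floor: "Within each school at least 30 students will be selected". Larger grades: "For larger schools, 20 per cent of students in the selected grade are selected". Twenty per cent exceeds 30 only when n > 30/0.20 = 150.
- Grade size, Table 1 (N, mean, SD): "Students 169 79.0 58.4".
- Baseline: students "present on the day of baseline were interviewed for a total of 8,276 students", in 133 schools.

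**Assumptions, not in the SAP**
- Students in Table 1 is read as the size of the target grade.
- Grade sizes follow a gamma distribution (a lognormal as a check).
- The outcome gradient is varied from 0.05 to 0.30 outcome SD per SD of grade size.

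**Reproducing the plan's figures.** The arm means in Table 2 give (66+94+78+71+86)/5 = 79.0, as in Table 1. Within-arm plus between-arm variance gives an SD of about 58.9, against 58.4 stated. The baseline school count is 98+28+7 = 133, and 8,276/133 = 62.2 students per school.

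**Step 1: contribution per school.** Selected: s = min(n, max(30, 0.2n)). Not selected: u = n − s. A control school contributes n under footnote 4.

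| Grade size n | Selected s | Share | Not selected u | Control school |
|---|---|---|---|---|
| 30 | 30 | 100% | 0 | 30 |
| 60 | 30 | 50% | 30 | 60 |
| 150 | 30 | 20% | 120 | 150 |
| 300 | 60 | 20% | 240 | 300 |

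**Step 2: grade size of the average student on each side.** For all control students this is mean + SD²/mean = 79.0 + 58.4²/79.0 = 122. The other columns come from simulation.

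| Assumed sizes | Control, all | Selected | Not selected |
|---|---|---|---|
| Gamma, mean 79, SD 58.4 | 122 | 91 | 140 |
| Gamma, mean 62.2, SD 46 | 96 | 71 | 116 |
| Lognormal, mean 62.2, SD 46 | 96 | 69 | 120 |
| Mean 62, coefficient of variation 0.5 | 78 | 64 | 90 |

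The SD of 46 keeps Table 1's coefficient of variation (58.4/79.0 = 0.74). In the first row the total-effect sides differ by 91 − 122 = −31 students, and −31/58.4 = −0.53 SD of size. If spillover uses all control students, the gap is 140 − 122 = +18, or +0.31 SD.

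**Step 3: bias without covariates** = gradient × gap in SD units (first row).

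| Gradient | Total | Spillover, if all controls |
|---|---|---|
| 0 | 0 | 0 |
| 0.05 | −0.03 | +0.02 |
| 0.10 | −0.05 | +0.03 |
| 0.20 | −0.11 | +0.06 |
| 0.30 | −0.16 | +0.09 |

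**Step 4: bias with linear adjustment for Students, gradient 0.20.** With exact size and a linear relation it is 0. With exact size but a logarithmic or step relation it is −0.02 to −0.04 (total) and +0.02 to +0.03 (spillover). If the error in Students has the same SD as size itself, it is −0.04 to −0.06 and +0.02 to +0.04. This step adjusts for Students alone, so Primary, Rural and the distances could absorb more.

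**Step 5: after the fix.** Weighting control students by s/n makes the average grade size 91 on both sides for the total effect. Weighting them by 1 − s/n makes it 140 on both sides for spillover. The expected size-related bias is then 0.

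**The case against.** The best defence is that the pre-specified model is adjusted. Equation (1) includes Primary, Rural, the distances and Students, and bias needs a dependence on grade size beyond all of them. The SAP reports no such dependence. This stands, so the bias is conditional. It does not remove the point: Students is noisy by the plan's own account and enters linearly, and the covariate-free check has no adjustment at all.

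The assumed size spread may also be too wide, since noise in Students would inflate its SD. With a coefficient of variation of 0.5 the total-effect gap falls from about −26 to −14 students. It does not vanish.

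A reader might infer three stronger points that the document does not support.

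- **A large bias from the mix of school types.** With 19 secondary and 114 primary schools and an assumed secondary grade size of 120, secondary students are 19×120/8,276 = 28% of all controls, but 19/133 = 14% of selected students. A 1 SD gap between grade 11 and grade 6 then shifts the unadjusted total effect by about −0.13 SD. That shift disappears in the planned model, because Primary is a covariate.
- **A biased spillover effect.** Footnote 4 is attached to the total effect. The spillover bias follows only if the undefined comparator is every control student. The firm finding there is the missing definition.
- **A distorted ranking of strategies.** The comparison that closes section 4.3 follows equation (2) without covariates. Differences between strategies there are differences between treated-arm means, so a shared control group cancels, and one selection rule applies to all three arms.

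**Conclusion.** The mismatch is real and follows from the text: near-equal school weights on the treated side and size-proportional weights on the control side of the random-arm total effect. The resulting bias is conditional. At an assumed gradient of 0.20 outcome SD per SD of grade size, it is about −0.1 SD in the covariate-free run. In the adjusted model it is about −0.02 to −0.06 SD if size is mismeasured or the relation is non-linear. With no gradient it is zero. These figures rest on the assumed gradient, the gamma shape and Table 1's spread.

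Spillover is biased the opposite way only if all control students are used. Treated grades of 30 or fewer would then contribute nobody, while control schools of that size would stay in; such schools make up about 13% to 27% under the assumed shapes.

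H1 and H2 concern overall effects, which use all students on both sides, so they are untouched. So is the covariate-free comparison between strategies. The point is of moderate severity: worth correcting because the correction is cheap, but not a threat to the main hypotheses.

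**What to change.** For random targeting only, amend footnote 4 and the spillover sentence in section 4.3 as follows.

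- Keep all control students. Compute p_j = min(1, max(30, 0.2n_j)/n_j) for each control school, with n_j taken from the baseline roster.
- Weight control students by p_j for the total effect.
- Define the spillover comparator as all control students weighted by 1 − p_j. Control schools with p_j = 1 then get weight zero, matching the treated schools that supply no unselected students.
- Use the same weights in the covariate-free robustness check.

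Leave the two centrality comparators on the plan's existing matching-share rule. The cost is a change of wording, one weight computed from rosters already collected, and a small loss of precision from weighting the controls.

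### The direct effect is described as a same-school contrast, but its pooled equation has no school term although the treated share falls with grade size

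*SAP*

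**What the plan says.** Section 4.3 defines the direct effect for the random-targeting arm only and explains its purpose: "By comparing treated to untreated students in the same school, this effect removes the indirect effect via peers". The model is set up with the words "except that we now restrict the sample to students in random-targeted schools, and estimate". What follows is a regression of the index on a common intercept, the individual treatment indicator T_ij and the covariate vector X_ij.

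Footnote 3 (section 4.1) lists X_ij. It holds ten school-level covariates, one of them Students, but no school indicator. Section 4.1 mentions school random effects only for an unspecified selection of robustness tests. Section 4.4 commits to a re-run of all analyses without covariates.

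Section 1 gives the selection rule: "Within each school at least 30 students will be selected. For larger schools, 20 per cent of students in the selected grade are selected". On Students, footnote 1 in section 2.1 warns that "the data behind this variable is highly noisy and based on estimates".

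**The concern.** A pooled coefficient on T_ij equals the same-school contrast only if the treated share is the same in every school, or if the covariates capture everything that varies with that share. The selection rule rules out the first. The second would need grade size to be measured exactly and modelled in the right form.

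Otherwise treated students come disproportionately from small grades, where most classmates are also treated, and untreated students from large grades. Two things then enter the estimate:

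- part of the peer effect that the text says is removed;
- any association between grade size and outcome.

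Separating direct from peer effects is the reason for this estimand, so the error goes to its meaning. The covariate-free re-run has no protection at all and could disagree with the main result for this reason alone.

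**Working it through.** **1. Treated share by grade size.** With exactly the minimum taken, p(n) = min(n, max(30, 0.2n))/n.

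| n | selected | share |
|---|---|---|
| 30 or fewer | all (inferred) | 100% |
| 40 | 30 | 75% |
| 60 | 30 | 50% |
| 100 | 30 | 30% |
| 150 | 30 | 20% |
| 200 | 40 | 20% |

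**2. Two schools by hand.** Take grades of 40 (30 treated, 10 not) and 150 (30 treated, 120 not), a true direct effect of 0, and a mean that is d higher in the small grade.

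- Treated students: 30 of 60 are in the large grade, mean -0.5d.
- Untreated students: 120 of 130 are in the large grade, mean -0.923d.
- Pooled estimate: -0.5d + 0.923d = 0.42d. With a school indicator it is 0.

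If d comes only from peers, d = (0.75 - 0.20)g = 0.55g, and the pooled estimate keeps 0.42 × 0.55g = 0.23g.

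**3. A full distribution of grade sizes.** Inputs from the SAP:

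- "present on the day of baseline were interviewed for a total of 8,276 students", in 133 schools (section 3.1): mean 8,276/133 = 62.2.
- Students has mean 79.0 and SD 58.4 (Table 1): recorded SD rescaled to 58.4/79.0 × 62.2 = 46.0.

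Assumptions: gamma-distributed sizes; classical noise in Students with reliability 0.7, so true SD = 46.0 × √0.7 = 38.5; true direct effect 0.

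*Peer part.* Without covariates the multiplier on g is the share of T_ij variance that lies between schools, 0.219. This agrees with the mean treated share of 0.57 in treated students' grades and 0.35 in untreated students' grades (0.57 - 0.35 = 0.22). With noisy Students in the model it is 0.116. With error-free Students it is still 0.08 (true SD 38.5) to 0.11 (true SD 46.0), because 30/n is not linear in n. For assumed g of 0.1 to 0.3 SD, the bias is +0.01 to +0.03 SD with Students and +0.02 to +0.07 without.

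*Size part.* Mean grade size is 67 for treated and 102 for untreated students, a gap of 35/38.5 = 0.91 SD. A gradient of 0.1 SD per SD of size therefore gives about -0.09 without covariates. Results at that gradient (they scale linearly; a negative gradient reverses the sign):

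| Model | Bias |
|---|---|
| No covariates | -0.092 |
| Students, reliability 0.5 | -0.041 |
| Students, reliability 0.7 | -0.025 |
| Students, reliability 0.9 | -0.008 |
| Students, error-free | 0.000 |
| Students (0.7) plus a covariate sharing 40% of size variance | -0.021 |
| Gradient in log size, Students at 0.7 | -0.032 |
| Gradient in log size, Students error-free | -0.020 |

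**4. Finite sample.** With 33 schools (98 treated schools over three arms) and Students at reliability 0.7, the mean estimates were:

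| Setting | Pooled | School fixed effects | Random effects plus Students |
|---|---|---|---|
| Gradient 0.1 | -0.026 | 0.001 | -0.005 |
| Gradient 0.2 | -0.052 | -0.001 | -0.009 |
| Gradient 0.3 | -0.075 | 0.001 | -0.011 |
| g = 0.3, no gradient | +0.027 | -0.005 | +0.003 |

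The -0.005 arises because a treated student has one fewer treated classmate. Randomization inference that redraws students within schools rejected in 5.0% and 3.7% of trials at gradients 0.1 and 0.3. Its reference distribution was centred at -0.025 and -0.076, so it corrects the test but not the point estimate.

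**5. Two related places in section 4.3.** Footnote 4 gives both centrality arms a matching share of controls, but for the random arm it reads: "under random targeting, we compare randomly targeted students in treated schools to all students in untreated schools". Treated students are again weighted towards small grades and controls are not. At gradients of 0.1 to 0.3 the random-arm total effect is off by -0.01 to -0.04 SD with Students and by -0.05 to -0.15 without. Separately, the plan says "the direct effect can only be estimated with random targeting", yet goes on: "We compare the effectiveness of targeting strategies on the total, spillover, and direct effect at the school level". The direct effect cannot be in that comparison.

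**The case against.** The direct effect is not one of the four questions listed in section 1; it appears only in section 4.3 and for one arm. The largest biases belong to the covariate-free re-run, not the main model. With Students, the peer part is at most about half of the SD of the pooled estimate (0.060 in the simulation), and the size part reaches that SD only near the top of the assumed gradients. Nine further school covariates may absorb some of the bias, and with a positive gradient the two parts partly cancel. School random effects, if applied here, would leave almost nothing.

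Some inputs are also inferred. The rule states a minimum, so 75% at grade size 40 supposes that exactly 30 are taken. The mean of 62.2 counts students present on the baseline day, not enrolment.

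Most of this stands as a limit on size. It does not remove the mismatch between text and equation. The plan does not commit the random-effects tests to the direct effect. The inferred inputs matter little to the main model: with sizes from Table 1 or from the random arm in Table 2, the peer multiplier with Students stays at 0.107 to 0.118, although without covariates Table 1 sizes give 0.18g rather than 0.22g.

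**Conclusion.** The concern holds. That the equation is not the comparison described, and that the treated share varies with grade size, follows from the document without any assumption beyond taking the selection rule at face value. The size of the bias does rest on assumptions, since the SAP gives no peer effect, size gradient or reliability. In the main model it is modest: about 0.12g from peers, and -0.02 to -0.07 SD for gradients of 0.1 to 0.3 SD at reliability 0.7. It is two to four times larger without covariates. The two parts can have opposite signs, so the direction is unknown. These are illustrations with Students as the main adjustment, not error rates of the full planned model. The overall-effect analyses under H1 and H2 use all students and are unaffected. This should be fixed, but it does not threaten the main conclusions.

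**What to change.** - Add school fixed effects to the direct-effect equation and keep them in the covariate-free re-run. School-level covariates then drop out of this model.
- State that schools with no untreated student contribute nothing, so the estimate applies to grades that have untreated students, and that fixed-effects least squares weights each school by n·p(1 - p).
- State that randomization inference for this effect redraws students within schools.
- Remove the direct effect from the comparison across targeting strategies.
- Minor: in the random-arm total effect, weight control students by p_j = min(1, max(30, 0.2n_j)/n_j). Define the spillover controls; if they are all control students, weight them by 1 - p_j. In the calculation these weights bring the bias to within 0.001 of 0.

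The cost is plan wording and a few lines of code. Grade sizes n_j can come from the attendance lists that section 3.2 says were collected at every school. If grades of 30 or fewer are fully treated, about 7 of 33 random-arm schools (21%), holding about 15% of treated students, drop out of this estimate; with Table 1 sizes the share of schools is about 13%. They carry no same-school contrast in any case. Precision hardly changes: the SD of the estimate is 0.051 with fixed effects against 0.060 pooled at an assumed between-school SD of 0.3, and about 0.050 against 0.048 at 0.05 to 0.10.

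### The between-strategy comparison of total and spillover effects drops the matched controls, so it mixes differences in JIC effect with differences between the kinds of students selected

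*SAP*

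**What the plan says.** For the total effect of a strategy, SAP section 4.3 will "restrict the samples to treated students in treated schools and comparable untreated students in control schools". Footnote 4 gives each strategy its own control set. For random targeting: "under random targeting, we compare randomly targeted students in treated schools to all students in untreated schools". For indegree targeting: "under indegree targeting, we compare treated students in indegree-treated schools to the corresponding share of highest-indegree students in untreated schools". Edge-centrality targeting has an analogous rule. Spillover is also defined against comparable control-school students, but footnote 4 does not say which ones.

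To compare strategies on these effects, the same section proceeds "by estimating models analogous to equation (2) without covariate controls on the appropriately restricted samples". Equation (2) (section 4.2) enters one indicator per targeting arm, with control schools as the common reference. The plan reads the comparison from the fitted coefficients: "differences between the elements of β_1 evaluate the differences between targeting strategies".

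The plan attaches a caution: "since the subsamples of treated (or untreated) individuals in the three targeting arms are not comparable", unadjusted comparisons are causal only at the group level, and covariate control is needed to read them as averages of individual effects. The covariates (footnote 3 to section 4.1) are school characteristics and student demographics A1 to A9. Neither a centrality measure nor the baseline index is among them.

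**The concern.** The estimation step and the comparison step do not fit together. The first compares central students with central students and random with random. The second puts all arms against one reference and subtracts coefficients, so the reference disappears along with the matching.

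If well-connected students would differ in knowledge or reported behaviour without any JIC, that difference enters the contrast as if it were an effect of targeting. It enters with opposite signs in the two comparisons: targeted students in a centrality arm are the more central part of the grade, and untargeted students are the less central remainder. With a positive correlation, centrality targeting would look too good for participants and too poor for their peers.

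At stake is part of the fourth research question in section 1, which asks for the best strategy for the overall, total and spillover effects. The last two are exposed.

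**Working it through.** The plan states no figure on this point, so there is none to reproduce.

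**Algebra.** With one intercept, three arm indicators and no covariates, least squares gives

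- b_ind = mean(Y, selected students, indegree arm) - mean(Y, control students)
- b_rand = mean(Y, selected students, random arm) - mean(Y, the same control students)
- b_ind - b_rand = mean(Y, indegree selected) - mean(Y, random selected)

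The last line is the same whichever control students are included. Its expectation is (tau_ind - tau_rand) + (mu0_central - mu0_all), where tau is the JIC effect in the students concerned and mu0 the mean outcome without the JIC. The second bracket is the unwanted part. For spillover it becomes (mu0_non-central - mu0_all).

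**Inputs for the size.**

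- Grade size: 8,276 students in 133 schools (section 3.1), so 8,276 / 133 = 62.2.
- Share selected: at least 30 per school (section 1), so 30 / 62.2 = 48.2%. The 20% rule exceeds 30 students only in grades above 30 / 0.20 = 150, so 20% is the lowest share. In a grade of 30 or fewer everyone is selected and the problem vanishes.
- Correlation r between centrality and the untreated index (SD 1): not in the documents. Assumed 0 to 0.3; negative values mirror the results.

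**Formula.** If centrality is roughly normal, the selected share p lies phi(z)/p SD above the grade mean in centrality and the rest phi(z)/(1-p) SD below. At p = 0.482 these are 0.826 and 0.770; at p = 0.20 they are 1.40 and 0.35. Multiplying by r gives the false gap, indegree minus random, in SD of the index when the true effects are equal:

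| r | Total, 48% | Spillover, 48% | Total, 20% | Spillover, 20% |
|---|---|---|---|---|
| 0 | 0 | 0 | 0 | 0 |
| 0.1 | +0.083 | -0.077 | +0.140 | -0.035 |
| 0.2 | +0.165 | -0.154 | +0.280 | -0.070 |
| 0.3 | +0.248 | -0.231 | +0.420 | -0.105 |

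**Simulation check.** The set-up was 33 random, 33 indegree and 35 control schools, 62 students per grade, 30 selected, an assumed school SD of 0.3, equal true effects in both arms and 400 runs per scenario.

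- The coefficient difference equalled the raw mean difference to within rounding (about 2e-15) in every run.
- At r = 0, 0.1, 0.2 and 0.3 the average gap was -0.004, +0.086, +0.169 and +0.250 for the total effect, and +0.006, -0.073, -0.152 and -0.233 for spillover (Monte Carlo standard error about 0.004).
- Taking each arm against control students picked by the same rule, and then differencing, gave -0.003 to +0.007 (total) and -0.004 to +0.007 (spillover).

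**The case against.** **The plan discloses the problem.** Schools were randomised, so the difference in mean outcome among those selected under each rule is a legitimate group-level consequence of assigning that rule, and section 4.3 claims no more for the unadjusted result. This stands: a reader might infer that the authors overlooked the non-comparability, and the text shows they did not. The caution limits the interpretation but does not change what is estimated. The contrast is one of outcomes, whereas the effects defined earlier in the section are differences from matched controls.

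**The model may be meant differently.** The restricted samples could be the three control sets of footnote 4. That is possible, but a single intercept cannot represent three references, and no strategy-specific intercepts are specified.

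**Covariates may help.** A reader might infer that adjustment achieves nothing. The documents do not support that: age, gender, religion, parental background or language may be related to centrality and absorb part of the gap. Adding a covariate to the simulation left the gap unchanged, but that covariate was unrelated to centrality by construction, so the result says nothing about the listed ones. What remains is that full removal is not assured.

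**The size is assumed.** This also stands. No correlation is given, zero gives no bias, and the share selected varies between schools. The normal formula is an approximation for indegree and does not describe the edge-betweenness arm, where section 3.2 says that students are chosen jointly as a group.

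**Conclusion.** The concern holds for the comparison of strategies on total and spillover effects. As written, that comparison cannot separate a difference in JIC effect from a pre-existing difference between the students selected; the group-level caution and the listed covariates do not ensure separation. The mechanism applies to edge-betweenness targeting too, though its size there was not calculated.

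The size is unknown. For indegree versus random at 48% selected, an assumed correlation of 0.1 to 0.3 gives about +0.08 to +0.25 SD (total) and -0.08 to -0.23 SD (spillover). It is zero at zero correlation and reverses sign if the correlation is negative. At a 20% share the total-effect gap is larger and the spillover gap smaller.

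A reader might go further and conclude that the targeting hypothesis itself is compromised. It is not: H2 concerns the overall effect in all students of randomised schools, where no selection enters. The separate strategy-specific effects keep their own control groups and are also unaffected. This is a correction to make to one set of secondary comparisons before analysis.

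**What to change.** Replace the comparison model in section 4.3 with a difference of matched contrasts.

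- For each strategy, take the students in that arm minus the control-school students picked by the same rule. Footnote 4 supplies the rule for the total effect. For spillover, state the complementary control students: those the centrality rule would not have selected and, for random targeting, all control students.
- Test differences between these contrasts in one stacked regression with strategy-specific intercepts. Cluster errors by school, which also covers control students who appear in more than one set.
- Add the baseline index as a covariate; the questionnaire was administered at baseline.
- Do not rely on centrality as a covariate. Indegree-targeted students occupy the upper range and untargeted ones the lower, so overlap between arms is limited and the adjustment would lean on extrapolation.

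The cost is wording and modest coding, since footnote 4 already requires centrality in control schools. Standard errors rise somewhat because control sampling error no longer cancels fully: by about 1 to 4% in the simulation (for example 0.00444 / 0.00431 = 1.03 for the total effect at r = 0), under its assumed school SD of 0.3. The result still compares effects in different kinds of students, and the plan should say so.
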